14.2 SECONDARY ENDPOINTS

Using Kaplan-Meier methods, we will estimate the probability distribution of progression-free survival and the time to recurrence. Results will be summarized by point estimates (12 months) with 95% CI. Exploratory analyses of these secondary objectives will compare the two treatment arms using the log rank test. Fisher's exact test will be used to compare frequency distributions of toxicity grades between the two arms.

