3 PATIENT SELECTION

3.1 ELIGIBILITY CRITERIA

3.1.1 Inclusion Criteria

- 3.1.1.1 Patients must have histologically confirmed localized high grade (G3) transitional cell carcinoma (urothelial carcinoma) of the bladder that is stage Ta, T1, and/or CIS

confirmed by the Laboratory of Pathology, NCI 90 days prior to study entry. This can be obtained at an outside hospital prior to entry into the study or at the NCI. However, all outside pathology specimens will require that the formalin-fixed paraffin embedded tissues be re-read by the Laboratory of Pathology, NCI. For patients enrolled at collaborating trial sites, diagnosis must be confirmed by the Department of Pathology at the institution where the patient is enrolled on the trial. Pathology can also be reviewed by the Laboratory of Pathology at the NCI if the participating trial site prefers another pathologic evaluation.

- 3.1.1.2 Patients have failed at least one previous induction course of intravesical BCG, defined as histologically confirmed persistent or relapsing tumor present on post-BCG endoscopic evaluation. All BCG failures will be considered for inclusion into the study, including BCG-refractory, -resistant, and -relapsing, as defined in the “Rationale and Background.” For the purposes of the study, “BCG-refractory” and “BCG-resistant” subjects will be considered to have “BCG-persistent” disease.
- 3.1.1.3 Patients who are not currently candidates for radical cystectomy (e.g. patient refuses surgery, comorbidities preclude major surgery, etc.).
- 3.1.1.4 Age ≥ 18 years.

Because no dosing or adverse event data are currently available on the use of BCG in combination with PANVAC™ in patients <18 years of age, children are excluded from this study.

- 3.1.1.5 ECOG performance status ≤ 2 (see Appendix A, Section 17.1).

- 3.1.1.6 Patients must have normal organ and marrow function as defined below:

- absolute neutrophil count	$\geq 1,500/\text{mcL}$
- platelets	$\geq 50,000/\text{mcL}$
- total bilirubin	$\leq 1.5 \times$ institutional upper limit of normal
- AST(SGOT)/ALT(SGPT)	$\leq 3 \times$ institutional upper limit of normal
- estimated GFR (calculated using CKD-EPI equation)	$\geq 30 \text{ mL/min}/1.73 \text{ sq.m.}$

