5.7 DURATION OF FOLLOW UP

Subjects will be followed for 1 year after the initial 20 week study course is completed with surveillance cystoscopy or until death, whichever occurs first.

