12.1.1.3 Recurrence-free survival

The recurrence-free survival duration will be measured from the start of TICE BCG therapy (week 3) until disease recurrence or death due to any cause in each arm. Recurrence is suspected and/or determined by urine cytology and/or cystoscopic exam and then confirmed pathologically after a TURBT. Positive cytology in the absence of pathologic confirmation is not considered to be a recurrence.

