12.1.1.4 Progression-Free Survival

PFS is defined as the duration of time from start of treatment to time of progression or death, whichever occurs first. The duration of progression-free survival is measured from the start of TICE BCG therapy (week 3) until progression or death due to any cause in each study arm. Progression is defined as upstaging from a lower stage to a higher stage (e.g., Ta to T1 or T1 to T2-4; or any N+ or M+ in these high grade tumors).

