12.1.1.5 Time to Tumor Recurrence

The duration of time measured from the start of TICE BCG therapy (week 3) until recurrence is noted.

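### Section 14.2 gives a 12-month Kaplan-Meier figure for time to recurrence without saying how deaths before recurrence are handled; on the usual reading it slightly overstates the probability of recurrence

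*Combined protocol and SAP*

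**What the plan says.** Section 14.2 sets the method: "Using Kaplan-Meier methods, we will estimate the probability distribution of progression-free survival and the time to recurrence". It then fixes the summary, "Results will be summarized by point estimates (12 months) with 95% CI", and the arm comparison, "Exploratory analyses of these secondary objectives will compare the two treatment arms using the log rank test".

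The endpoint definitions are in Section 12.1:

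- Time to tumor recurrence (12.1.1.5): "The duration of time measured from the start of TICE BCG therapy (week 3) until recurrence is noted". Death is not mentioned.
- Recurrence-free survival (12.1.1.3) runs from the same starting point "until disease recurrence or death due to any cause in each arm".
- Progression-free survival (12.1.1.4): "PFS is defined as the duration of time from start of treatment to time of progression or death, whichever occurs first".

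Follow-up under Section 5.7 lasts one year after the 20-week course "with surveillance cystoscopy or until death, whichever occurs first", and Section 5.8.2 lists death as a reason to leave the study. Inclusion criterion 3.1.1.3 admits patients who are not candidates for cystectomy. Its examples are refusal of surgery and that "comorbidities preclude major surgery".

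The document has no rule for a death without recurrence in the time-to-recurrence analysis, and it names no competing-risk method.

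**The concern.** Of the three time-to-event endpoints, time to recurrence is the only one whose definition leaves death out. A patient who dies without recurrence can no longer recur. If that death is censored, Kaplan-Meier treats the patient as still able to recur later, at the same rate as those who remain under observation. The complement of the curve then answers how often recurrence would be seen if nobody died. A reader of a 12-month recurrence figure will normally take it as the proportion of patients who actually recur.

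The two quantities differ as soon as one patient dies first. In a population that includes people unfit for major surgery, that can be foreseen. What is at stake is one descriptive percentage per arm and its interval, not a decision of the trial.

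**Working it through.** **Step 1: the plan's own figures.** Section 14.2 states no number for time to recurrence, so I checked the Section 14.1 rates used below. Under exponential survival HR = ln(S_BCG)/ln(S_combination):

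- subgroup 1: ln(0.375)/ln(0.65) = 2.277
- subgroup 2: ln(0.20)/ln(0.447) = 2.00
- subgroup 3: ln(0.48)/ln(0.65) = 1.70

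All three agree with the plan. With the 1:5:1 mix, equal allocation, 49 patients, the stated accrual (1 per month for 6 months, then 2 per month) and analysis at month 40, expected events are 40.0 (stated 40). Simulated power for the one-sided 15% log-rank test is 85.2% (stated 84%). The rates are a sound base.

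**Step 2: inputs.**

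- 12-month RFS, BCG alone: 37.5%, 20%, 48%. BCG+PANVAC: 65%, 44.7%, 65% (Section 14.1).
- Subgroup weights: 1/7, 5/7, 1/7 (Section 14.1).
- d, the 12-month risk of death absent recurrence: **an assumption**, because the document gives none. The main range is 3-10%, with 1-20% for sensitivity. It is taken as the same in all subgroups and both arms, with constant hazards.

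**Step 3: formulas, per subgroup, over 12 months.**

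- total hazard L = -ln(RFS)
- death hazard D = -ln(1 - d)
- recurrence hazard R = L - D
- 1-KM with deaths censored = 1 - exp(-R)
- actual probability of recurrence (cumulative incidence) = (R/L) × (1 - RFS)

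**Step 4: worked case, d = 10%, so D = 0.1054.**

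| Arm, subgroup | L | R | 1-KM | Cumulative incidence |
|---|---|---|---|---|
| BCG, 1 | 0.9808 | 0.8755 | 58.3% | 55.8% |
| BCG, 2 | 1.6094 | 1.5041 | 77.8% | 74.8% |
| BCG, 3 | 0.7340 | 0.6286 | 46.7% | 44.5% |
| Combination, 1 and 3 | 0.4308 | 0.3254 | 27.8% | 26.4% |
| Combination, 2 | 0.8052 | 0.6998 | 50.3% | 48.1% |

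Weighted 1:5:1, this gives 70.6% against 67.7% with BCG alone and 43.9% against 41.9% with BCG+PANVAC.

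**Step 5: across assumed death risks (1-KM vs cumulative incidence; excess in percentage points from unrounded values).**

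| d | BCG alone | Excess | BCG+PANVAC | Excess |
|---|---|---|---|---|
| 1% | 73.2 vs 72.9 | 0.3 | 49.0 vs 48.8 | 0.2 |
| 3% | 72.7 vs 71.8 | 0.9 | 47.9 vs 47.3 | 0.6 |
| 5% | 72.1 vs 70.7 | 1.4 | 46.8 vs 45.8 | 1.0 |
| 10% | 70.6 vs 67.7 | 2.8 | 43.9 vs 41.9 | 2.0 |
| 20% | 66.9 vs 61.3 | 5.6 | 36.9 vs 33.4 | 3.5 |

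The excess in the between-arm difference is the gap between the two columns: about 0.2 points at 3% and 0.8 at 10%.

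**Step 6: the other reading.** If deaths were counted as events, 1-KM would equal 1 - RFS. With BCG alone the weighted RFS is (37.5 + 5 × 20 + 48)/7 = 26.5%, so 1-KM would be 73.5%, against an actual 70.7% at d = 5%. That is an excess of 2.8 points, compared with 1.4 under censoring.

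**Step 7: scale.** The 95% half-width for a proportion p with n patients is 1.96 × sqrt(p(1-p)/n). It is 16.3 points for p = 0.75, n = 27 and 20.0 points for p = 0.5, n = 24.

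**The case against.** - **Censoring of deaths is inferred.** This stands. A reader might take the plan to prescribe censoring, but no section does. What the document supports is that the handling is unspecified. Both handlings overstate recurrence, so the direction does not depend on the inference.
- **Overstatement depends on the quantity wanted.** Section 14.2 promises the distribution of time to recurrence and does not say that death should be taken into account. The censored curve does estimate recurrence in the absence of death, provided death is unrelated to recurrence risk. This also stands: the fault is the mismatch between that quantity and the ordinary meaning of a 12-month recurrence percentage.
- **Nothing important rests on it.** RFS, which Section 14.1 tests, counts death, and so does PFS. Time to recurrence is not among the secondary objectives in Section 1.2, and 14.2 calls its arm comparison exploratory. The log-rank test remains valid as a comparison of cause-specific hazards. A reader might infer that the primary analysis or this test is compromised; neither is.
- **The death rate may be low.** Comorbidity is only one example of a route into the trial, beside refusal of surgery, and no split is given. ECOG above 2 is excluded (3.1.1.5), as are symptomatic heart failure, unstable angina and active second malignancy that would interfere with treatment (3.1.2.7), and significant cardiomyopathy or infarction or stroke within a year (3.1.2.14). Inferring a population selected for grave illness with many early deaths goes beyond the text. With 24.5 patients per arm, the model expects only 0.4-1.4 deaths before recurrence within 12 months with BCG alone and 0.5-1.9 with BCG+PANVAC at d = 3-10%. At 3%, the chance that an arm has none is about 66% and 58% respectively, and the two estimators then coincide.
- **No general rule links the excess to the recurrence rate.** It is larger with BCG alone at the planned rates. With D = 0.1054, however, it peaks at about 3.0 points near a recurrence hazard of 2 and falls to 2.3 at a hazard of 4.

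These points limit the size and reach of the concern. They do not supply the missing rule or make 1-KM the probability of recurrence.

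**Conclusion.** The concern holds as a small, cheap improvement. The plan fixes an estimator and a 12-month summary for an endpoint that leaves death out, and it gives no rule for deaths without recurrence. Under either handling, the complement of the Kaplan-Meier curve exceeds the actual 12-month probability of recurrence if anyone dies first.

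For an assumed death risk of 3-10%, the excess under censoring is about 0.9-2.8 points with BCG alone and 0.6-2.0 with BCG+PANVAC. Even at 20% it stays well below the interval half-width of roughly 16-20 points. These sizes rest on the Section 14.1 rates, constant hazards, a death hazard common to both arms, and a death risk the document does not supply. The tempting stronger conclusion, that the trial's efficacy result is biased, has no support: both RFS and PFS count death.

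**What to change.** In Section 14.2, state that for time to recurrence the 12-month cumulative incidence of recurrence will be reported for each arm (Aalen-Johansen estimator, 95% CI), with death without recurrence as a competing event. Keep the log-rank test, labelled as a comparison of cause-specific recurrence hazards, or use Gray's test. Keep Kaplan-Meier for RFS and PFS.

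This takes one sentence and a standard routine, with no additional data, because deaths are already needed for RFS. The cost is a slightly lower recurrence figure that is less comparable with older reports based on Kaplan-Meier; the Kaplan-Meier estimate can be shown beside it if that comparison matters.

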1 OBJECTIVES

1.1 PRIMARY OBJECTIVE

1.1.1 To determine if there is an improvement in disease-free survival (DFS*) with BCG + PANVAC compared with BCG alone in a phase II study in non-muscle invasive high-grade urothelial carcinoma of the bladder who have failed to respond to intravesical BCG. *within 1 year post treatment

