5.2.2.3 Between weeks 17-20 (+/- 7 days), a CT urogram and chest x-ray prior to biopsy, a planned cystoscopy, EUA, and TURBT will be done of previous tumor area and of any new areas of tumor. Tissue will be sent for pathology and be formalin-fixed paraffin embedded. If possible, some tissue will also be frozen.

- If a suspicious lesion is identified, it will be biopsied. If recurrent tumor is not found, then the subject will return every 3 months for a surveillance cystoscopy as per standard-of-care. If recurrent tumor is found, the patient has met the primary endpoint of recurrence and will be taken off study.

5.2.2.4 At every surveillance cystoscopy post-treatment up to 12 months, urine may be collected for cytology as well as for immune-related markers along with blood through 6 green top tubes for correlative immunologic aims.

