11 STUDY CALENDARS

Evaluations below may be performed within \pm 5 days of indicated time in order to accommodate patient schedules, holidays and weather emergencies.

A) STUDY CALENDAR FOR BCG + PANVAC ARM

	Baseline (On study)	Week 0	Week 3	Week 4	Week 5	Week 6	Week 7	Week 8	Week 11	Week 15	Week 17- 20	Follow- up ¹⁰
BCG			X	X	X	X	X	X				
PANVAC-V ¹		X										
PANVAC-F ¹			X				X		X	X		
NIH Advanced Directives Form ¹¹	X											
History and Physical ²	X		X	X	X	X	X	X	X	X	X	X
CBC with differential ³	X										X	X ^o
Chemistry ^{3,4}	X										X	X ^o

Abbreviated Title: Vaccine and BCG for bladder ca

Version Date: 05/22/2025

	Baseline (On study)	Week 0	Week 3	Week 4	Week 5	Week 6	Week 7	Week 8	Week 11	Week 15	Week17- 20	Follow- up ¹⁰
PT, PTT ³	X										X	X ^o
PPD (Research)	X										X	
Urinalysis ⁵	X		X	X	X	X	X	X		X	X	
Urine Cytology ⁶	X										X	X
Urine (Research) ⁷		X	X*		X*						X	X ^o
Immunology (Research blood) ⁸		X	X					X	X	X	X	X ^o
Serum Beta- HCG ⁹	X											
Biopsy											X	X
Chest X-ray	X										X	
CT urogram	X										X	

B) STUDY CALENDAR FOR BCG ONLY ARM

	Baseline (On study)	Week 0	Week 3	Week 4	Week 5	Week 6	Week 7	Week 8	Week 11	Week 15	Week17- 20	Follow- up ¹⁰
BCG			X	X	X	X	X	X				
NIH Advanced Directives Form ¹¹	X											
History and Physical ²	X		X	X	X	X	X	X		X	X	X
CBC with differential ³	X										X	X ^o
Chemistry ^{3,4}	X										X	X ^o
PT, PTT ³	X										X	X ^o
PPD (Research)	X										X	
Urinalysis ⁵	X		X	X	X	X	X	X			X	X

	Baseline (On study)	Week 0	Week 3	Week 4	Week 5	Week 6	Week 7	Week 8	Week 11	Week 15	Week 17- 20	Follow- up ¹⁰
Urine Cytology ⁶	X										X	X
Urine (Research) ⁷			X*		X*						X	X ^o
Immunology (Research blood) ⁸		X	X					X			X	X ^o
Serum Beta- HCG ⁹	X											
Biopsy											X	X
Chest X-ray	X										X	
CT urogram	X										X	

¹ Applies only to treatment arm 2 (BCG + PANVACTM). Panvac administration continues as planned regardless of any delays in BCG administration.

*These time periods should correspond to BCG instillations #1 and #3, respectively. If a postponement of an instillation occurs, urine collection will occur after instillations #1 and #3 irrespective of the trial week. On these weeks, urine will be collected twice: first collection will be prior to BCG instillation and second collection of urine will be 2 hours after drainage of BCG.

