² Baseline: H & P and laboratory studies should be completed within 28 days of initiating treatment. This will include determination of ECOG performance status.

³ Baseline laboratory studies should be completed within 28 days of initiating treatment.

⁴ Chemistry panel: Na+, K+, Cl-, CO₂, glucose, BUN, creatinine, albumin, calcium, magnesium, phosphorus, alkaline phosphatase, ALT, AST, total bilirubin, pre-albumin, and LDH.

⁵ Urinalysis: If prior to an operative procedure, then will be obtained within 2-21 days of surgery and with an accompanying urine culture. If prior to BCG administration, a simple urinalysis will be performed in the hospital on the day of administration. ***Urine will be tested weekly prior to each BCG administration and the presence of gross hematuria or a urinary tract infection by urinalysis will result in holding that week's BCG dose as specified in the protocol.

⁶ Urine cytology: will be obtained from voided urine within 2-21 days of operative procedures OR through instrumentation at the time of an operative procedure

⁷ Urine (research): Urine will be obtained for correlative immune studies checking for chemokine and cytokine levels

⁸ Blood will be obtained for immunologic/research assays. CTC analysis, plasma and sera will be isolated to look for CD4 antigen-specific responses, CD8 antigen-specific responses, and flow cytometry profiles of various immune cell types.

⁹ In females of child-bearing age, Beta-HCG to be done at baseline within 48 hours prior to receiving vaccinia

¹⁰ These patients will be followed every 3 months for 1 year after the completion of the initial 20 week study course with standard of care for non-muscle invasive high grade bladder cancer. This includes urinalysis, urine cytology, cystoscopy, possible bladder biopsy, and medical assessments. For patients unable to complete every 3 month follow-up at the NIH or CINJ after week 20, we will keep them on study and obtain their outside pathologic records and labs from their outside urologists who will perform these evaluations.

¹¹ As indicated in section **15.3**, all subjects will be offered the opportunity to complete an NIH advanced directives form. This should be done preferably at baseline but can be done at any time during the study as long as the capacity to do so is retained. The completion of the form is strongly recommended, but is not required. Participating sites should adhere to appropriate procedures specific to their site.

X^o = optional

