12.1.1.2 Evaluable for objective response

Only those patients who have biopsy-proven disease present at baseline, have received at least one cycle of therapy (6 or fewer weekly intravesical doses of BCG), and have had their disease re-evaluated will be considered evaluable for response. These patients will have their response classified according to the definitions stated below.

In order to compare the secondary outcomes between study arms, all durations will be measured from the start of TICE BCG therapy (week 3). This is the start of therapy for the TICE BCG arm alone. BCG is not started at week 0 for two reasons: 1) to allow adequate healing from previous TURBT and 2) allow vaccinia priming vaccine to be given to combination group at week 0 with enough recovery time to possibly make the administration of BCG in week 3 safer in these patients. Furthermore, by following this schema, patients in each group will start BCG at the same time after study entry.

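### The 12-month estimate of time to recurrence is read one to four weeks before a scheduled look, so in each arm it describes recurrences found by about week 40-43

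*Combined protocol and SAP*

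**What the plan says.** Section 14.2 covers two endpoints by Kaplan-Meier: "we will estimate the probability distribution of progression-free survival and the time to recurrence". It then asks for a reading at one time: "Results will be summarized by point estimates (12 months) with 95% CI".

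Section 12.1.1.2 sets the time origin for secondary outcomes: "all durations will be measured from the start of TICE BCG therapy (week 3"). Under 12.1.1.5, time to recurrence stops when recurrence is noted. Section 12.1.1.3 requires pathology for a recurrence: "Positive cytology in the absence of pathologic confirmation is not considered to be a recurrence".

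The looks are set in two places. Section 5.2 gives the first: "Between weeks 17-20 (+/- 7 days), a CT urogram and chest x-ray prior to biopsy, a planned cystoscopy, EUA, and TURBT". Footnote 10 of the study calendars gives the rest: "These patients will be followed every 3 months for 1 year after the completion of the initial 20 week study course". The calendars allow a tolerance of plus or minus "5 days of indicated time in order to accommodate patient schedules".

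The primary objective (1.1.1) describes its window differently, as "within 1 year post treatment". Neither Section 12 nor Section 14.2 says how to treat events found between looks, or which visit stands for 12 months.

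**The concern.** Recurrence enters the data only when someone looks. A Kaplan-Meier curve on detection dates is flat between looks and drops at each one. If the reading time falls just before a drop, the curve still shows the level of the previous look, here about three months old. The figure would be labelled 12 months but would describe an earlier time, and would look too favourable.

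In a small phase II trial, each arm's 1-year rate is the number that readers carry to other 1-year results. The trial also has a second one-year figure, in the primary objective, with its own wording for the window. If the two are read at different looks, they will not agree.

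**Working it through.** **Reproducing the plan's figures.** Section 14.1 gives 1-year recurrence-free survival (RFS) of 37.5%, 20% and 48% on BCG alone and 65%, 44.7% and 65% on BCG+PANVAC, exponential, in the ratio 1:5:1.

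- HR = ln(S control)/ln(S combination) = 2.277, 2.00 and 1.70, as stated.
- Expected events with 49 patients: 39.7 with 27.5 months of accrual, 40.0 with 28 (stated: 40).
- Simulated one-sided 15% log-rank power, 10,000 runs: 85.1% unstratified, 86.2% stratified (stated: 84%).

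The planning model is reproduced closely enough to use below.

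**When the looks fall.** Weeks from BCG start = study week − 3, with 13 weeks per quarter.

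| Visits counted from | First look | Q1 | Q2 | Q3 | Q4 |
|---|---|---|---|---|---|
| week 20 | 17 | 30 | 43 | 56 | 69 |
| a week-17 evaluation | 14 | 27 | 40 | 53 | 66 |

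Twelve months is 365.25/7 = 52.2 weeks. The last look before it is at week 40-43 and the next is at week 53-56, about 1 to 4 weeks too late.

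**Size for recurrence.** The curve at 12 months equals event-free survival at the last look, week k: S(k) = Σ w·S(1 year)^(k/52.18), with w = 1/7, 5/7, 1/7. The RFS rates stand in for recurrence rates, since no others are given.

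- True 12-month value, BCG alone: (0.375 + 5×0.20 + 0.48)/7 = 26.5%. BCG+PANVAC: (0.65 + 5×0.447 + 0.65)/7 = 50.5%.
- k = 43, BCG alone: (0.446 + 5×0.266 + 0.546)/7 = 33.1%, over by 6.6 points. BCG+PANVAC: 56.8%, over by 6.3.
- k = 40: 35.7% and 59.1%, over by 9.2 and 8.6 points.

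A simulation of look-detected events with the 5-day tolerance gives 6.5 and 6.3 points when visits run from week 20, and 7.8 and 7.3 when they follow an evaluation spread over weeks 17-20. If the first evaluation also uses its 7-day margin, the averages are 7.4 and 7.0, and about 4% of patients have the next look inside 12 months.

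**Sensitivity to the hazard.** Assume Weibull times with the same 1-year rates: S(k) = Σ w·S(1 year)^((k/52.18)^shape). Across both arms and k = 40 to 43, the overstatement is 4.5-6.4 points at shape 0.7 and 3.2-4.5 at shape 0.5.

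**Progression-free survival.** No rate is stated. Under a constant hazard and assumed true 12-month values, with all events found at looks, the overstatement is 4.5-6.1 points at 70%, 3.2-4.3 at 80% and 1.7-2.2 at 90%.

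**Between-arm difference.** True: 50.5 − 26.5 = 24.0 points. At week 43: 23.7. At week 40: 23.4.

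**Reading after the third quarterly look.** S(53) to S(56) is 26.0-24.2% on BCG alone and 50.0-48.1% on BCG+PANVAC, within about 2.4 points of the 12-month value.

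**The case against.** The strongest reply is that the endpoint is recurrence when noted, and for that endpoint Kaplan-Meier at 12 months is correct. The overstatement exists only against the time at which disease would have been detectable. This is formally right. But a reader takes a 12-month recurrence-free rate to mean the state at 12 months, and the plan does not say that the figure reflects a look about three months earlier.

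The planning rates come from cited studies and may themselves rest on detection dates. A reader might infer that a control arm behaving as planned would look better than its benchmark. The documents do not show how those rates were measured, so that inference is not made here.

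The size also depends on a constant hazard. Six in seven patients are expected to be BCG-persistent or to have failed repeatedly within that group, and all are biopsied at weeks 17-20, so early detection is plausible. That stands, and it is why the lower range is given.

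The practical stakes are limited. The arm comparisons in 14.2 are exploratory, no decision rule uses the 12-month value, and with 24-25 patients per arm the approximate 95% half-width is 17-20 points. Even so, a shift of 6-9 points is about 0.6 to 1.0 standard error (about 9 points on BCG alone, 10 on BCG+PANVAC), in the same direction in both arms, and avoidable.

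**Conclusion.** The mismatch follows from the text, and the upward shift in each arm's 12-month recurrence estimate is real. It is about 6-9 points under the plan's rates, mix and constant hazard, with 6.5 the better figure if visits run from week 20, and about 3-6 points under the front-loaded hazards assumed above.

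Four stronger readings are tempting but not supported:

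- **That 6-9 points applies to every event-free estimate.** No progression-free rate is given, deaths are dated exactly, and Section 15.4 places muscle-invasive progression more often after 2 years. For that endpoint the size is unknown and probably smaller.
- **That the treatment comparison is biased.** The difference changes by 0.3-0.6 points.
- **That no patient has the third quarterly look within 12 months.** An evaluation at week 16, allowed by the 7-day margin, puts it at 16 − 3 + 39 = 52 weeks.
- **That the primary window ends at study week 60 on BCG and 67 on PANVAC, counting from last dose.** This is one reading. Sections 5.7 and 5.8.2 together suggest about week 72 in both arms. The documents show that the two one-year figures are worded on different clocks, not that they differ by a set number of visits.

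**What to change.** Leave the visit calendar as it is and change the analysis wording. In Section 14.2, do one of the following:

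- Define the 1-year landmark as the third quarterly visit, about 13 months from BCG start. Assign events to nominal visits and read the estimate after that visit's window closes.
- Report an interval-censored (Turnbull) estimate at 12 months. That estimator does not fix the curve inside an interval between looks, so state the interpolation rule in advance.

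Then reconcile the time origin and landmark with the window in 1.1.1, so that both one-year figures use one clock common to both arms.

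The cost is a few sentences, with no added visits or patients. The landmark is about 13 months rather than exactly 12, or the estimator is less familiar, and the reported event-free rate will be less favourable. Re-timing the surveillance visits is not needed and is not proposed.
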